Effectiveness of Lemon Essential Oil of Aromatherapy in Reducing Test Anxiety in Nursing Students Document Date: 01.01.2020

Methods

Context and Characteristics: A randomized, pre-test-post-test design was carried out to examine the effectiveness of lemon essential oil in reducing test anxiety in first-year students of the Faculty of Medical Sciences of a private university in Istanbul.

Universe and Sample: The universe of the study consists of first-year students of the Faculty of Medical Sciences of a private university in Istanbul (N=54), with active registration records at the university as of January 2020.

The sample included students who met the inclusion criteria (N=48) from among the students who agreed to participate in the study after it was announced. The randomisation of the study sample group was conducted through block randomisation. In the study, since the student names are available in the class lists, students are randomly assigned to the groups using the numbers table in this list with the help of the computer. The blocks were randomly selected and this procedure continued until all subjects to be included in the study were assigned to the groups. At the end of this procedure, the number of students in the groups was equalized and twentyfour students each were assigned to the intervention and control groups. Since two of the students in the intervention group did not want to participate in the study, they left the study without handing in their pre-test forms.

Inclusion and Exclusion Criteria: The inclusion criteria included not having a respiratory system disease (asthma, flu, etc.), known allergic reaction to the essential oil to be used, allergy to any smell, pregnancy, epilepsy, inability to smell or inhale, not using any medication that might affect heart rate and blood pressure, not practicing other complementary medical practices (yoga, meditation, aromatherapy, massages, etc.), volunteering to participate in the study.¹⁰⁻¹² Students determined to have an anxiety disorder, disease, allergic reaction in question, a recent stressful history or a disability condition that is thought to be effective on the results of the study were excluded in the study.

Data Collection Tools

The data were collected through the personal information form, State Test Anxiety Scale (STAS) and Test Anxiety Schedule (TAS).

Personal Information Form

The personal information form contained nine questions on age, gender, education level, profession, place of residence, socio-economic status and success level at school (According to the grade point average).

Test Anxiety Scale (TAS)

Developed by Bozkurt (2019), the scale evaluates the degree of anxiety students feel before a test on a scale of 0 to 10. A score of 0 indicates no anxiety, while a score of 10 indicates severe anxiety.³⁵

State Test Anxiety Scale

Developed by Şahin in 2019, this scale determines students' anxiety levels before a test. It is a 4-point Likert-type scale consisting of three sub-dimensions and 22 items. The cognitive dimension consists of nine items (3, 4, 7, 9, 14, 16, 18, 20, 22), wherein the lowest possible score is nine and the highest score is 36. The psychosocial dimension consists of five items (6, 10, 12, 13, 21), wherein the lowest possible score is 5 and the highest score is 20. The physiological dimension includes eight items (1, 2, 5, 8, 11, 15, 17, 19), wherein the lowest possible score is 8 and the highest score is 32. Possible scores on the scale ranged between 22 and 88. There were no reverse items on the scale. A high score on the sub-dimensions and the whole scale indicates high level of anxiety. Cronbach's alpha coefficients of the scale were 0.93 for the cognitive sub-dimension, 0.84 for the psychosocial sub-dimension, 0.85 for the physiological sub-dimension and 0.94 for the whole scale.³ Cronbach's alpha coefficient in this study was 0.78 for the cognitive sub-dimension, 0.82 for the psychosocial sub-dimension, 0.87 for the physiological sub-dimension and 0.91 for the whole scale.

Application of Data Collection Tool

The study was carried out prior to an anatomy examination, which was the most concerning for the students according to their expressions. The pretest personal information form, STAS and TAS data collection tools were administered to all students in the study in a different exam room. Students in the control group were taken to the exam room prepared for them and were told that there would be no study application other than administering the data collection forms. Anything related to aromatherapy that can affect the process was not told to the students. Next, students in the intervention group who agreed to participate in the study were informed about the aromatherapy method to be used. Students in the intervention group were taken to the exam room specially prepared for them. After waiting for 15 minutes in the exam room for the aromatherapy administered through inhalation to take effect in the intervention group, the posttest STAS and TAS data collection tools were administered. There was no intervention for the students in the control group. The study was carried out on the basis of the application made at the universities during the exam periods of the students. At the universities where the students study, 15 minutes before the exam, the students are taken to the class, the seating arrangement is provided and information is given about the exam rules. This is a standard practice for all students. Since the study was conducted according to this application, after waiting 15 minutes in the exam hall, post-test STAS and TAS data collection tools were administered.

Intervention

The exam rooms were cleaned and adequately ventilated before the administration. Students in the intervention and control groups were taken to two separate exam rooms with the same size and physical features. The intervention group was placed in a classroom where the doors and windows were shut 30 minutes prior to the test, and an oil diffuser was placed to diffuse the fragrance. The oil diffuser was placed 30 cm away from the students, and five (5) drops of essential lemon essential oil (diluted with 100cc distilled water) were placed inside the diffusing chamber. To ensure homogeneity of the fragrance in the air, the diffuser was activated 15–20 minutes before the intervention group was taken to the exam room. Furthermore, three drops of lemon essential oil were applied to non-absorbent napkins before the students were taken to the exam room. These napkins were placed on the students' collars, and the intervention group was taken to the examination hall. Students in the intervention group were asked to inhale the lemon essential oil in the examination hall for 15 minutes.¹⁰⁻¹² Students are admitted to the class 15 minutes before the exams in the practice carried out during the exam period at the university where the research is conducted. In the study, a 15-minute application period was determined by taking both the relevant studies and this exam application.

Fifteen minutes later, the STAS and TAS data collection tools were administered to the intervention group. The data collection tools took approximately five minutes to fill out, and the researchers recollected them after completion. After the data collection tools were retrieved, the oil diffuser and napkins placed on the students' collars were removed from the exam room, following which the test commenced.

To prevent cross-contamination, the students in the control group were taken to a cleaned and ventilated exam room located away from the students in the intervention group. After waiting for 15 minutes in the exam room, STAS and TAS data collection tools were administered. The data collection tools took approximately five minutes to fill out, and the researchers recollected them after completion, following which the test commenced. Lemon essential oil was used as the aromatic oil in this study administration.

Variables

The independent variable in this study was lemon essential oil, and the dependent variables were STAS and TAS. Lemon essential oil was obtained from a company that has safety, quality and approval certificates from the Turkish Ministry of Health. This oil, which does not contain any artificial preservatives, is derived from lemon peels using the mechanical process of cold pressing.

Data Analysis

The descriptive statistics were shown through numbers and percentages, while the pretest and post-test data were shown through mean scores and standard deviation values in the analysis of the data. The Wilcoxon test, Student T-test, Mann Whitney U-test and Spearman's correlation analysis were used. A simple linear regression analysis was used to determine the effect of the independent variable on the dependent variable. The data were analysed on a computer using SPSS 22. The statistical significance level was set as p < 0.05.

Ethical Dimension

An approval (No. 2020/1) was obtained from the Ethics Committee of the University where the study was conducted, and written permission was obtained from the institution where the study would be carried out. Moreover, written and verbal consent was obtained from the participants after explaining the purpose of the study. The written permission was also obtained from the researcher who conducted the Turkish validity and reliability study of the scale.

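### No between-arm result is made decisive for effectiveness, so within-arm pre-post p-values, which cannot show that the oil works, remain usable as evidence

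*Combined protocol and SAP*

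**What the plan says.** The design is described under Context and Characteristics: "A randomized, pre-test-post-test design was carried out to examine the effectiveness of lemon essential oil". Under Universe and Sample, "twentyfour students each were assigned to the intervention and control groups", and then "two of the students in the intervention group did not want to participate in the study" and left before handing in pre-test forms. That leaves 22 v 24.

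Under Application of Data Collection Tool, all students complete both scales at pre-test. The timing of the repeat follows the university's usual exam routine: "after waiting 15 minutes in the exam hall, post-test STAS and TAS data collection tools were administered". The Intervention section gives the control arm the same wait and the same repeat of the scales.

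Data Analysis names "The Wilcoxon test, Student T-test, Mann Whitney U-test" and Spearman correlation. It adds a simple linear regression for the effect of the independent variable, which the Variables section defines as the lemon oil, with STAS and TAS as dependent variables. It closes with "The statistical significance level was set as p < 0.05". No test is linked to an outcome or to a between-arm or within-arm comparison, no primary comparison is named, and no pre-test term is mentioned for the regression.

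**The concern.** Mann-Whitney, the two-sample rank test, is listed separately, and every student is measured twice. Wilcoxon therefore most naturally means the signed-rank test of pre-test against post-test inside each arm. The Student t-test might also be used in its paired form; the plan does not say.

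A within-arm test answers whether scores changed over time. Retesting, settling into the room and the approaching exam can all change scores, and they act in both arms. A significant fall in one arm with a non-significant fall in the other is not a test of the difference between the arms. Because the plan does not restrict the conclusion to the between-arm contrast, a report could cite that pattern as evidence of benefit and still be consistent with the plan.

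The error can also go the other way. If the oil prevented a rise in anxiety that occurred in control, the oil arm would show no fall, and its within-arm test would miss the benefit.

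**Working it through.** The plan gives no sample-size, power or effect-size figure, so there is nothing of its own to reproduce beyond the counts: 24 + 24 = 48 and 24 − 2 = 22.

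**Inputs from the documents.** 22 oil and 24 control students; significance level 0.05.

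**Assumptions.** Two-sided tests (sidedness is not stated); normal change scores; one outcome; no oil effect; the same true mean change d in both arms, in SDs of change. The documents give no value for d, so it is varied from 0 to 1.0.

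**Formula.** Let P_n(d) be the chance that a within-arm test with n students is significant. The arms are independent, so

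Pr(significant in oil, not in control) = P_22(d) × [1 − P_24(d)].

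With the normal approximation, P_n(d) = Φ(d√n − 1.96) + Φ(−d√n − 1.96). The maximum is at d = 0.403, where P_22 = 0.472 and P_24 = 0.506, giving 0.472 × 0.494 = 0.233. The noncentral t gives a maximum of 23.2% at d = 0.42. With 24 v 24 the maximum would be 0.5 × 0.5 = 25%.

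**Simulation of the signed-rank test** (100,000 trials per row, normal-approximation p-values, counting only oil-arm changes in the direction of the shared fall), beside two-sided between-arm tests on change scores:

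| Shared fall d | Oil arm significant | Control significant | Oil only | Between-arm t | Mann-Whitney on change |
|---|---|---|---|---|---|
| 0 | 5.0% | 4.9% | 2.4% | 5.0% | 4.9% |
| 0.2 | 14.1% | 15.0% | 11.7% | 4.9% | 4.8% |
| 0.3 | 26.1% | 27.6% | 19.0% | 4.9% | 4.6% |
| 0.4 | 41.9% | 44.8% | 23.2% | 4.9% | 4.7% |
| 0.5 | 59.3% | 63.0% | 21.9% | 5.1% | 4.8% |
| 0.6 | 75.0% | 78.5% | 16.1% | 4.9% | 4.8% |
| 0.8 | 93.9% | 95.6% | 4.1% | 4.9% | 4.8% |
| 1.0 | 99.1% | 99.5% | 0.5% | 5.1% | 4.9% |

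The peak is 23.2% to 23.5%, near d = 0.4. The between-arm tests reject in 4.6% to 5.1% of trials at every d. Half of that, about 2.5%, is in the direction of benefit.

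**Two scales.** If a claim on either STAS or TAS counted, the simulated rate at d = 0.42 would be 33%, 37% or 41% for assumed correlations of 0.8, 0.5 and 0 between the two change scores.

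**Reverse case.** If controls rose by 0.8 SD and the oil fully prevented it, the oil-arm signed-rank test would show a significant fall in only about 2% to 3% of trials. A between-arm test of change would have about 75% power.

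**Why the regression is protected.** A change shared by everyone adds the same constant to every post-test score. In a regression of post-test on arm and pre-test, that constant enters the intercept and leaves the arm coefficient unchanged.

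**The case against.** The strongest reply is that the harmful rule is not in the documents. Nothing says that effectiveness will be concluded from significance in one arm only. The one sentence about effect points to a regression of the scales on the oil, which on its natural reading compares the arms, and Mann-Whitney and the t-test can compare them too. This stands. A reader might infer that the plan discards the randomised comparison, and the documents do not support that. The tools are present; what is missing is a statement that one of them decides.

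A reader might also take it as certain that Wilcoxon means the paired test. That is likely, but it remains an inference, and it should not single out Wilcoxon, since the t-test could be used the same way.

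Finally, 23% is a worst case that needs both arms to become calmer by about 0.4 SD in the minutes before the exam the students feared most. With no shared change the rate is about 2%. With a shared rise, a significant fall in the oil arm alone would be rarer still. This also stands, and it is why the range matters more than the peak. The mirror reading, a significant rise in control only, could mislead under a shared rise, but its rate was not calculated for this note.

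None of this removes the gap. Adding a better between-arm model would not by itself stop within-arm p-values being cited as evidence.

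**Conclusion.** The point holds as a gap in the plan: no between-arm result is made decisive, and within-arm tests cannot support an effectiveness claim. If the one-arm-only reading were used, the false-claim rate for a single outcome would run from about 2% (no shared fall) through 12% (0.2 SD) to about 23% (near 0.4 SD), then back to 4% (0.8 SD), against about 2.5% in that direction for a between-arm test of change. These figures assume 22 v 24 students, normal changes, two-sided 0.05 and no oil effect.

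The documents do not support reading 23% as this trial's false-positive rate. They neither adopt nor exclude the rule, and they give neither the size nor the direction of the shared change. The arithmetic is secure; whether the results would be read this way is not known. The change should be made, because it bears on the main claim and costs little.

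**What to change.** In Data Analysis, state what each listed test is for, and add that effectiveness is concluded only from the between-arm difference in post-test STAS (and TAS). Estimate that difference from the linear regression already planned, with arm and the pre-test score as covariates, and report it with a 95% CI. Report within-arm pre-post changes, and any paired-test p-values (Wilcoxon or paired t), as descriptive only.

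The pre-test term mainly improves precision. What removes the error described here is confining the conclusion to the between-arm difference. Which scale takes precedence still has to be settled separately.

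The cost is one or two sentences and a re-run in SPSS on data already collected. Within-arm p-values could then no longer be cited as evidence of benefit.

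### The effect of lemon oil is estimated by a one-predictor regression, with no pre-test adjustment and no choice between post-test and change score, so precision is lost

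*Combined protocol and SAP*

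**What the plan says.** The opening of Methods describes the design: "A randomized, pre-test-post-test design was carried out to examine the effectiveness of lemon essential oil". Under Universe and Sample, "twentyfour students each were assigned to the intervention and control groups". Two intervention students then withdrew, and "they left the study without handing in their pre-test forms". That leaves 22 against 24.

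The Application of Data Collection Tool section confirms a baseline measurement: "The pretest personal information form, STAS and TAS data collection tools were administered to all students in the study in a different exam room". Every remaining student should therefore have a pre-test score on both scales.

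The Variables section defines the quantities to be related: "The independent variable in this study was lemon essential oil, and the dependent variables were STAS and TAS". No time point is attached. The Data Analysis section then states: "A simple linear regression analysis was used to determine the effect of the independent variable on the dependent variable". It also lists "The Wilcoxon test, Student T-test, Mann Whitney U-test" and Spearman's correlation, without tying any of them to an outcome or a contrast. The only use it states for the pre-test and post-test data is to show means and standard deviations. It names no ANCOVA, multiple regression or mixed model.

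**The concern.** In a randomised trial with a baseline on the same scale as the outcome, the baseline is usually the best available means of reducing residual variation. A simple regression on group cannot use it as a covariate. If the outcome is the post-test score, the pre-test is ignored. If the outcome is the change score, the pre-test enters with its coefficient forced to 1, which is less efficient than estimating the coefficient. The text allows both readings.

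Two things are at stake in a trial of 46 students. One is the width of the interval around the effect. The other is an unrecorded choice between two outcomes that can give different answers. A side issue is the Wilcoxon test. If it is the paired pre/post test within each arm, which is likely but not stated, it can be significant without any effect of the oil, because a change common to both arms is enough.

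**Working it through.** **Inputs.** From Universe and Sample: 24 − 2 = 22 lemon oil, 24 control, 46 in total. From Data Analysis: significance level 0.05, taken here as two-sided. The documents give no sample-size calculation, target effect, SD or pre/post correlation, so there is no figure of the plan's own to reproduce. Assumed: equal pre-test and post-test SDs (set to 1), a pre/post correlation ρ of 0.3, 0.5, 0.7 or 0.8, and a 0.5 SD effect for power.

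**Step 1: what the simple regression is.** With a two-level group variable, the slope is the difference in means and its test is the equal-variance t-test on 44 df. On a simulated dataset the two p-values were identical (0.01898). The pre-test therefore contributes only if the outcome is a change score.

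**Step 2: standard errors.** The common factor is √(1/22 + 1/24) = 0.295. Multiply it by:

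- post-test only: 1 (44 df)
- change score: √(2(1 − ρ)) (44 df)
- ANCOVA: √((1 − ρ²)(1 + 1/42)) (43 df), where 42 = 46 − 4 and the second bracket is the cost of estimating the pre-test slope

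At ρ = 0.5 the post-test SE is 0.295. The change-score SE is √1 × 0.295 = 0.295. The ANCOVA SE is √(0.75 × 1.024) × 0.295 = 0.259.

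**Step 3: power and precision** (noncentral t; each cell reads post-test / change / ANCOVA).

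| ρ | Power at 0.5 SD (%) | Detectable at 80% power (SD) | 95% CI half-width (SD) |
|---|---|---|---|
| 0.3 | 38 / 29 / 40 | 0.85 / 1.00 / 0.82 | 0.59 / 0.70 / 0.57 |
| 0.5 | 38 / 38 / 47 | 0.85 / 0.85 / 0.74 | 0.59 / 0.59 / 0.52 |
| 0.7 | 38 / 57 / 63 | 0.85 / 0.65 / 0.61 | 0.59 / 0.46 / 0.43 |
| 0.8 | 38 / 75 / 78 | 0.85 / 0.53 / 0.51 | 0.59 / 0.38 / 0.36 |

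ANCOVA gains 2 to 40 points over post-test scores (40 − 38; 78 − 38). Over change scores it gains 3 to about 12 points (78 − 75 at ρ = 0.8; 40.4 − 28.8 before rounding at ρ = 0.3). Without the slope cost the ANCOVA powers would be 41, 48, 64 and 79%. A simulation of 6,000 trials per ρ, with chance baseline imbalance included, gave 40, 48, 63 and 77%.

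**Step 4: beyond the assumed range.** At ρ = 0.15, ANCOVA and post-test only both have 38% power. At ρ = 0.9, ANCOVA and change score both have 96%. But one loss is small only where the other is large: at ρ = 0.2 the change score has 26% against ANCOVA's 39%, and at ρ = 0.9 post-test only has 38% against 96%.

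**Step 5: error rates.** With no effect, each method alone rejected in 4.6 to 5.8% of 4,000 simulated trials per ρ. If either the post-test or the change-score test may be declared the result, rejection rises to about 9%. At a 0.5 SD effect the two tests disagree on significance in 28% of trials at ρ = 0.3, rising to nearly half at ρ = 0.8.

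**Step 6: the Wilcoxon test, if it is within-arm.** Assume no oil effect and a common fall of 0.2, 0.4 or 0.5 SD of the change score (5,000 simulated trials each). The lemon arm is significant in 13, 40 and 58% of trials. The lemon arm alone is significant in 11, 23 and 22%, and the control arm alone in 13, 26 and 27%.

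**The case against.** A group regression on post-test or change scores is a legitimate randomised comparison, so the plan is not invalid and the dispute is partly about efficiency. The size of the gain cannot be fixed from the documents. The 40-point end needs both ρ = 0.8 and the post-test reading; at the same ρ the change-score reading loses only 3 points. The two measurements use the same scales around a 15-minute wait, so a high correlation is plausible, and if change scores were in fact used little may have been lost.

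All of that stands as a limit on magnitude. It does not rescue the plan, because the text does not say which outcome was used, and across 0.3 to 0.8 ANCOVA is at least as precise as either.

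Other objections stand in part:

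- The 5% error rate holds only for an outcome fixed in advance. Leaving it open gives that up, which is a further reason to name one model.
- Each arm sat in its own single room, so room and treatment cannot be separated. ANCOVA does not cure this, and the intervals above count student-level variation only. It affects every candidate analysis equally.
- The role of the Wilcoxon test is inferred, so Step 6 is conditional and secondary.
- TAS is a bounded 0 to 10 score, so a linear model needs a residual check.

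**Conclusion.** The concern holds. The effect of the oil is assigned to a one-predictor regression, the outcome is not identified as post-test or change, and no pre-test-adjusted model is named although the data for one were collected. The consequence is lost precision and an open analysis choice, not bias. Under equal SDs and ρ between 0.3 and 0.8, the detectable effect falls from 0.85 SD on post-test scores, or from 1.00 to 0.53 SD on change scores, to between 0.82 and 0.51 SD with ANCOVA. The textual gap is certain. The size of the loss depends on a correlation the documents do not give, and could be negligible for one of the two readings at either end of the range. It should be fixed, because the remedy is nearly free.

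**What to change.** For STAS total and for TAS separately, replace the simple regression with a linear model of post-test score on group and the same scale's pre-test score. Report the adjusted mean difference with its 95% CI, and base the conclusion about effectiveness on that between-arm estimate. Check the residuals, particularly for TAS.

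State which outcome and contrast the t-test and the Mann-Whitney test serve; the latter could be a between-arm sensitivity analysis. If the Wilcoxon test compares pre-test with post-test within an arm, say so and keep it as description.

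The State Test Anxiety Scale section already reports reliability from this study's own data ("alpha coefficient in this study was 0.78 for the cognitive sub-dimension"). If ANCOVA is adopted after the data were seen, label it post hoc, report the regression now described beside it, and state which outcome that regression used.

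The cost is one or two sentences and one degree of freedom. No new data are needed, and the model runs in the SPSS version already named.

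### STAS and TAS are unranked outcomes under one 0.05 level, and no rule says which result, or combination of results, would show that the oil works

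*Combined protocol and SAP*

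**What the plan says.** Variables: "the dependent variables were STAS and TAS". Neither scale is called primary and no order is given.

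Data Analysis: several tests are listed without being assigned to an outcome, followed by "A simple linear regression analysis was used to determine the effect of the independent variable on the dependent variable" and "The statistical significance level was set as p < 0.05". No section gives a multiplicity adjustment, sidedness, a testing order or a definition of success.

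The two instruments are close in purpose. Under Test Anxiety Scale (TAS), "the scale evaluates the degree of anxiety students feel before a test on a scale of 0 to 10". The State Test Anxiety Scale (STAS) has 22 items, a total of 22 to 88 and three sub-dimensions, and also measures anxiety before a test. Application of Data Collection Tool has both scales completed by all students at pretest and again after the 15-minute wait, when "the posttest STAS and TAS data collection tools were administered".

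Two other statements bear on the remedy:

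- The State Test Anxiety Scale section reports reliability from the study's own data ("alpha coefficient in this study was 0.78 for the cognitive sub-dimension"), so at least some scale data had been seen when this text was written.
- Intervention states: "Students in the intervention and control groups were taken to two separate exam rooms".

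**The concern.** The stated aim in Methods is to examine whether the oil is effective in reducing test anxiety. Two outcomes are tested for that aim, each at the full 0.05, and the plan does not say how the two results combine into one conclusion. If they agree, little turns on it. If one is significant and the other is not, the plan supports a positive conclusion, a negative one or none, depending on a rule that is not written down. As written, either scale could carry the effectiveness claim after the results are seen, and a reader could not attach an error rate to it.

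**Working it through.** **Plan's own figure.** The only one is the 0.05 level. One two-sided test at that level has a 5% false-positive rate, which simulation reproduces (4.99% to 5.01%). The plan gives no family-wise rate, power or sample-size calculation to reproduce.

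**Inputs from the document**
- Two dependent variables (Variables) and a level of 0.05 (Data Analysis).
- Group sizes from Universe and Sample: 24 assigned per group, and two left the intervention group before handing in pretest forms, so 24 − 2 = 22 against 24.

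**Assumptions, because the document is silent**
- No true effect; students independent; two-sided tests; bivariate normal scores.
- One pooled t test per scale with 22 + 24 − 2 = 44 df, which is the same test as simple linear regression of score on group.
- STAS-TAS correlation ρ of 0.5 to 0.95, since both scales rate anxiety before a test and are filled in at the same sitting.

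**Error rate under each possible rule.** The link between the rules is P(either) = 0.05 + 0.05 − P(both). With ρ = 0, P(either) = 1 − 0.95² = 9.75%. For other ρ the joint distribution was simulated (4,000,000 draws per value):

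| ρ | Either significant | False claim of reduction on either | Both significant | Holm, any rejection |
|---|---|---|---|---|
| 0 | 9.75% | 4.94% | 0.25% | 4.94% |
| 0.5 | 9.12% | 4.56% | 0.89% | 4.67% |
| 0.7 | 8.37% | 4.18% | 1.61% | 4.32% |
| 0.8 | 7.86% | 3.94% | 2.15% | 4.05% |
| 0.9 | 7.06% | 3.53% | 2.91% | 3.63% |
| 0.95 | 6.50% | 3.25% | 3.51% | 3.33% |

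The benchmark is 5%, except for the false claim of reduction, where it is 2.5%. At ρ = 0.5 the identity gives 10% − 0.89% = 9.11%, which agrees with the table. The large-sample bivariate normal formula, 1 − P(|Z₁| < 1.96 and |Z₂| < 1.96), gives 9.07% at 0.5 and 6.46% at 0.95. If each test were one-sided at 0.05, the either-scale rate would be 8.8% to 6.3%.

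**Power cost of Holm, no pretest adjustment.** Noncentrality = d × √(22 × 24 / 46) = 0.846 × 3.388 = 2.866. With 44 df the power is 80.0% at 0.05 and 70.6% at 0.025. The second figure is for Holm's first step. If both scales share this effect, power per scale under the full Holm procedure is 76.1% at ρ = 0.5 and 74.0% at ρ = 0.95.

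**Power with the pretest as covariate.** Adjustment divides the residual SD by 1/√(1 − r²), where r is the pretest-posttest correlation (not given, so assumed). Put the other way, the noncentrality becomes 2.866 / √(1 − r²), with 43 df. At the 0.025 level:

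| r | Noncentrality | Power |
|---|---|---|
| 0.3 | 2.866 / 0.954 = 3.00 | about 75% |
| 0.5 | 2.866 / 0.866 = 3.31 | about 83% |
| 0.7 | 2.866 / 0.714 = 4.01 | about 95% |

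The formula ignores chance imbalance in pretest scores, so these values are slightly optimistic.

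**The case against.** The strongest reply is that the inflation belongs to a rule the document does not contain. A reader might infer that the trial runs at a 9% error rate. The text does not support that: if both scales must be significant, the rate is below 5%. This reply stands. What is established is that the rule is missing; inflation is one of its possible consequences.

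The correlation is not in the document either. The upper end of the assumed range is extreme. With the STAS alpha of 0.91 reported from this study, taken as reliability and with uncorrelated errors, the observed correlation cannot exceed √0.91 = 0.954 even if TAS had no measurement error. So 6.5% is the favourable end rather than a likely value. That qualifies the range but does not remove the inflation under an either-scale rule.

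A reader might also infer selective reporting, or read the singular wording in the regression sentence as a sign of one undisclosed main outcome. Neither is supported. Both scales are named as dependent variables and collected in both groups, nothing says that only one would be reported, and the singular can be generic wording for each outcome in turn. If both results are reported, a reader can apply an adjustment. The reader still would not know what the plan counts as success, and an effectiveness aim needs that.

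Finally, other weaknesses may matter more: treatment is confounded with room, and the listed tests are not assigned to outcomes. This is fair. The percentages here exclude both, and the STAS sub-dimensions too.

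**Conclusion.** The point holds in conditional form. The plan has two unranked outcomes, one unadjusted level and no success rule, so the error rate of its main conclusion depends on a choice left open. Under an either-scale rule, multiplicity alone adds about 1.5 to 4 percentage points (6.5% − 5% and 9.1% − 5%); under a both-scales rule the rate is 0.9% to 3.5%. The omission is certain from the text. The percentages rest on the assumed correlation range, two-sided testing, normal scores, independent students and 22 against 24 analysed. They are not estimates of the total error rate for an oil effect, because each group sat in its own room and the choice among tests is not counted.

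**What to change.** 1. For STAS total and for TAS, make the between-group comparison of posttest scores by linear regression on group, with that scale's pretest score as covariate. This extends the simple regression already listed and uses pretest data already collected.
2. Apply Holm across the two p-values: the smaller against 0.025 and, if that is met, the larger against 0.05. Base the effectiveness conclusion on the adjusted result, and show both unadjusted estimates with confidence intervals.
3. Label STAS sub-dimension results exploratory.
4. Label the rule post hoc unless it can be shown to predate sight of the outcome data. The label discloses that the test and the rule were chosen late; it does not control for that choice.
5. State beside the conclusion that each group sat in its own room, so Holm controls multiplicity only and does not separate an oil effect from a room effect.

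Cost: changes to analysis wording and reporting, with no new data. Without pretest adjustment, an outcome with 80% power at 0.05 has about 71% at Holm's first step. With adjustment, power at 0.025 is about 75%, 83% or 95% for assumed pretest-posttest correlations of 0.3, 0.5 or 0.7. A post hoc label also weakens the claim that can be made.
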